10.0 EFFICACY ANALYSES

The efficacy analyses will be based on the mITT Population. Baseline for efficacy is defined as the last nonmissing efficacy assessment before the first dose of study treatment. All statistical tests will be 2-sided hypothesis tests performed at the 5% level of significance. All confidence intervals will be 2-sided 95% confidence intervals, unless stated otherwise.

For efficacy analyses in which study center is a factor, a small center will be defined as a center with fewer than 2 participants for at least 1 treatment group in the mITT Population. Small centers will be pooled to form pseudo-centers so that each treatment group includes at least 2 mITT participants within the center. Pooling will be done within each country using the following algorithm:

1. Based on the number of mITT participants, small centers will be ordered from the largest to the smallest, and centers of the same size will be ordered from the largest center number to the smallest center number.
2. The pooling process starts with the largest small center from the top, which will be pooled with the smallest from the bottom until a non-small center is formed.
3. The process will be repeated using the small centers left out after the first pass.

If any centers are left out at the end of the process, they will be pooled with the smallest pseudo-center. If there is more than 1 smallest pseudo-center, the pseudo-center with the smallest center number will be selected. In case that the pseudo center formed by pooling all small centers is still a small center, it will be pooled with the smallest non-small center. If there is more than 1 smallest non-small center, the one with the smallest center number will be selected.

The pseudo-centers will be used for all efficacy analyses when the model is adjusted for study center.

The rater-administered MADRS will be used for the efficacy analyses.

10.1 PRIMARY EFFICACY PARAMETER

The primary efficacy parameter will be the change from baseline in MADRS total score at 1 day after first dose and will be analyzed using a mixed-effects model for repeated measures (MMRM) model with treatment group, visit, pooled study center, and treatment group-by-visit interaction as fixed effects and the baseline value and baseline value-by-visit as covariates. An unstructured covariance matrix will be used to model the covariance of within-participant scores. If the model fails to converge based on the unstructured covariance matrix, then structures of Heterogenous Toeplitz, Toeplitz, and Compound Symmetry will be applied, in the specified order, until the model converges. The Kenward-Roger approximation will be used to estimate denominator degrees of freedom ([Kenward and Roger 1997](#)). These analyses will be performed based on all postbaseline scores using only the observed cases (OC) without imputation of missing values. MADRS assessments at all study visits will be included in the MMRM model. Primary endpoint descriptive statistics and associated statistical testing results from the MMRM model will be presented.

10.2 SECONDARY EFFICACY PARAMETER

The secondary efficacy parameter will be the change from baseline in MADRS total score at Day 8 and Day 9 after single oral dose, on Day 15 after repeated dose, and on Day 22, 7 days after the completion of AGN-241751 dosing. The primary analysis for the secondary endpoints will be performed using an MMRM with treatment group, visit, pooled study center, and treatment group-by-visit interaction as fixed effects and the baseline value and baseline value-by-visit as covariates. An unstructured covariance matrix will be used to model the covariance of within-participant scores. The Kenward-Roger approximation will be used to estimate denominator degrees of freedom ([Kenward and Roger 1997](#)). These analyses will be performed based on all postbaseline scores using only the OCs without imputation of missing values. The Day 1 predose MADRS will be used as baseline for all analysis. MADRS assessments at all study visits will be included in the MMRM model. Key secondary endpoint descriptive statistics and associated statistical testing results from the MMRM model will be presented by visit.

In addition, a sensitivity analysis using the multiple imputation (MI) approach under missing not at random (MNAR) assumptions will be performed on the primary and key secondary efficacy parameters.

For the sensitivity analysis of the primary endpoint, change from baseline in MADRS totals score at 1-day post Day 1 and secondary endpoint, change from baseline in MADRS totals score at Day 8, Day 9, Day 15, and Day 22, the following steps will be followed to generate datasets and analyze the data:

1. Generate the imputed datasets:

The implementation of the pattern-mixture model (PMM) with control-based pattern imputation of Ratitch and O'Kelly (2011) will be used to impute missing data under the MNAR assumption.

- Intermittent (non-monotone) missing data in both treatment groups are imputed using the Monte-Carlo Markov chain (MCMC) method under the MAR assumption.
- Remaining monotone missing data are imputed using a PMM approach using a sequential regression imputation model estimated based on data from the placebo arm only. 50 imputed datasets will be generated.

2. Model based key estimates LSMean difference between treatment group and standard error) will be obtained for the change from baseline in MADRS total score at day 2 (1 day after first dose), Day 8, Day 9, Day 15, and Day 22 for each imputed dataset using the same MMRM.
3. Calculation of the combined mean difference, 95% CI, and p-value for the change from baseline in MADRS total score at day 2 (1 day after first dose), Day 8, Day 9, Day 15, and Day 22 will be done using the method proposed by Rubin (1987) via PROC MIANALYZE.

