10.3.1.2. Primary Analyses (Part A and Part B)

The primary analysis for the primary and secondary endpoints in Part A and Part B will be performed using an MMRM with treatment group, visit, pooled study center, and treatment group-by-visit interaction as fixed effects and the baseline value and baseline value-by-visit as covariates. An unstructured covariance matrix will be used to model the covariance of within-participant scores. If the model fails to converge based on the unstructured covariance matrix, then structures of Heterogenous Toeplitz, Toeplitz, and Compound Symmetry will be applied, in the specified order, until the model converges. The Kenward-Roger approximation will be used to estimate denominator degrees of freedom ([Kenward and Roger 1997](#)). These analyses will be performed based on all postbaseline scores using only the OCs without imputation of missing values.

In addition, a sensitivity analysis using the MI approach under MNAR assumptions will be performed on the primary and secondary efficacy parameters.

Detailed methods and procedures for the above outlined missing data-derived sensitivity analyses will be documented in the final SAPs prior to the study database locks.

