Participants will have 7 study visits during the study. The first 6 visits will occur in the following pattern: the Screening Visit (Visit 1; up to Day -14); at Visit 2 (Day 1 of the randomized inpatient treatment); at Visit 3 (1 day following the inpatient treatment day); at Visit 4 (7 days following the first inpatient treatment day, which is the second inpatient treatment day); at Visit 5 (1 day following the second inpatient treatment day); and at Visit 6 (7 days following the second inpatient treatment day). If necessary, study visits may be conducted up to 2 days before or after the scheduled visits with the exception of visits that are 1 day apart (ie, Visits 2 and 3 must be conducted 1 day apart; and Visits 4 and 5 must be conducted 1 day apart). Participants will enter a 1-week safety follow-up period and return for Visit 7. Participants who prematurely discontinue from the study before completing the double-blind treatment should enter the 1-week safety follow-up period. Additional follow-up visits may be scheduled within 30 days, if necessary for safety reasons.

Figure 4-1

Study Design Diagram

FU = follow-up; IP = investigational product.

All treatments will be presented to participants as oral once daily dosing throughout the study.

At Visit 2 (Day 1 of the randomized inpatient treatment), all participants will be randomized to receive the first treatment, followed by blinded placebo on Days 2 through 7.

Starting at Visit 4 (Day 8), participants will then start 7 consecutive days of double blinded randomized treatment, administered once daily through Day 15.

The schedule of activities for Study 3125-104-002 is presented in [Table 4-1](#). The double-blind treatment period starts with the first dose of study (Day 1) treatment and ends with the last dosing day (Day 15).

Table 4-1 Schedule of Activities (SoA)							
		Double-blind Treatment Period					Safety Follow-up Period
Visit	Screening (1)	2	3	4	5	6/ET^a	7
Study Day	up to -14 days	1	2	8	9	15	22
Informed consent	x						
Medical (surgical, neurologic) and psychiatric histories	x						
Prior medication history	x						
Inclusion/exclusion	x	x					
Randomization assessment		x					
Clinical laboratory determinations ^b	x	x				x	
Urine drug screen	x					x	
Serum pregnancy test	x					x	
Pharmacogenomics consent and sample ^c				x			
Vital signs ^d	x	x	x	x	x	x	x
ECG	x					x	
Physical examination	x					x	
SCID	x						
MADRS	x	x	x	x	x	x	x
CGI-S	x	x	x	x	x	x	
BPRS+	x		x	x	x	x	
CADSS	x		x	x	x	x	

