6.0 PARTICPANT POPULATIONS

6.1 MODIFIED INTENT-TO-TREAT POPULATION

The modified intent to treat (mITT) population includes all randomized participants who received at least 1 administration of study treatment and have a baseline MADRS total score and at least 1 postbaseline assessment for the MADRS total score during the double-blind treatment period. Participants will be summarized according to the randomized study treatment.

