16.0 DATA HANDLING CONVENTIONS

16.1 VISIT TIME WINDOWS

Table 16-1 presents the visits assigned for efficacy and safety analyses and the corresponding range of treatment days (window) during which an actual visit may occur.

Table 16-1 Visit Time Windows

Derived Visit	Scheduled Visit Day^a	Window
Baseline	Screening/Day 1 (Visit 2)	last nonmissing assessment before Index1 ^a
Day 2	Day 2 (Visit 3)	Days (Index1 ^a +1, IndexA ^b -1)
Day 8	Day 8 (Visit 4)	IndexA ^b
Day 9	Day 9 (Visit 5)	Days (IndexA ^b +1, IndexA ^b +4)
Day 15	Day 15 (Visit 6)	Days (IndexA ^b +5, day of final double blind visit or ET Visit occurring after IndexA ^b +5)
End of Double-Blind Treatment	The last available post-baseline assessment (unscheduled assessments) during the double-blind treatment period	
Safety Follow-up (Day 22)	Days [Day after final double-blind visit or ET visit occurring after Day 15 (Visit 6)/Early Termination visit]	

a Index1: Day of first double-blind dose

b IndexA: Day of second double-blind dose, if not received, use Index1 + 7 days

If the assessment date (if the assessment date is unavailable, use visit date instead) is on or after the date of the first dose of study treatment, the study day is calculated by assessment date – date of the first dose of study treatment + 1. If the assessment date is before the date of the first dose of study treatment, the study day is calculated by assessment date – date of the first dose of study treatment. Therefore, a negative day indicates a day before the start of the study treatment.

If a participant has 2 or more visits within the same window, the last visit with a nonmissing value will be used for analysis.

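### In Part A, the promised MNAR sensitivity analysis cannot apply its placebo-based step to a missing Day 2 score, so its Day 2 result is in effect a second MAR analysis

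*SAP*

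**What the plan says.** The commitment comes from Protocol 10.3.1.2: "a sensitivity analysis using the MI approach under MNAR assumptions will be performed on the primary and secondary efficacy parameters". SAP 10.2, which covers Part A, repeats it and names the Day 2 primary endpoint. Its third step reports a Day 2 result from the imputed datasets: "Calculation of the combined mean difference, 95% CI, and p-value for the change from baseline in MADRS total score at day 2".

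The imputation has two branches:

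- Intermittent gaps: "Intermittent (non-monotone) missing data in both treatment groups are imputed using the Monte-Carlo Markov chain (MCMC) method under the MAR assumption".
- All other gaps: "Remaining monotone missing data are imputed using a PMM approach using a sequential regression imputation model estimated based on data from the placebo arm only".

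The second branch is the only one that departs from MAR. SAP 10.2 gives no delta adjustment, tipping-point analysis or other MNAR device for Day 2.

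The population is fixed in SAP 10.0: "The efficacy analyses will be based on the mITT Population". SAP 6.1 admits a dosed participant to mITT only with a baseline MADRS and "at least 1 postbaseline assessment for the MADRS total score during the double-blind treatment period". SAP 4.0 ends that period on the last dosing day, Day 15, so a Day 22 score alone does not qualify.

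Table 16-1 (SAP 16.1) fills the derived Day 2 value from any score between the day after the first dose and the day before the second double-blind dose. Its footnote covers a second dose that is never given: "IndexA: Day of second double-blind dose, if not received, use Index1 + 7 days".

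**The concern.** Each rule is ordinary when read alone. Together, the mITT entry condition and the intermittent/monotone split leave no Day 2 value for the placebo-based model to impute. The participants whose gap would be monotone from Day 2 are those with no score after baseline, and mITT excludes them.

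A report that follows the SAP would show a Day 2 difference, confidence interval and p-value under an MNAR label. A reader could take agreement with the primary MMRM as evidence that the primary endpoint withstands informative missingness. It would instead be agreement between two MAR analyses. Dosed participants with no double-blind MADRS after baseline, whose absence could be informative, are in neither analysis.

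**Working it through.** The plan states no figure on this point to reproduce. The check is a complete count of missingness patterns under the SAP's own rules.

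**Inputs.** Derived postbaseline visits: Days 2, 8, 9, 15 and 22 (Table 16-1). mITT: at least one of Days 2, 8, 9 and 15 observed (SAP 6.1 with 4.0). A missing visit is intermittent if any later visit is observed, and otherwise monotone (SAP 10.2).

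**Step 1: are there holes in the windows?** Taking the first dose as study Day 1, the Day 2 window runs from Day 2 to the second-dose day minus 1:

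- Second dose on Day 8, or not given (1 + 7 = 8): Days 2 to 7.
- Second dose on Day 6 or Day 10 (the permitted 2-day shift): Days 2 to 5, or Days 2 to 9.

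The Day 8, 9 and 15 windows follow without a break. Every double-blind score from the day after the first dose therefore falls in some derived visit. Only Day 1 itself has none, and Protocol 9.1.2 schedules the Part A Day 1 MADRS predose.

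**Step 2: patterns in mITT.** All patterns: 2^5 = 32. In mITT: (2^4 − 1) × 2 = 30. The 2 outside are nothing observed and Day 22 only.

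**Step 3: Day 2 missing within mITT.** At least one of Days 8, 9 and 15 must be observed, with Day 22 free: (2^3 − 1) × 2 = 14. Each has a later observed score, so the number with a monotone gap at Day 2 is 0.

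**Step 4: where the placebo-based step can act.**

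| Derived visit | mITT patterns with it missing | Of these, to the placebo-based step |
|---|---|---|
| Day 2 | 14 | 0 |
| Day 8 | 14 | 1 |
| Day 9 | 14 | 3 |
| Day 15 | 14 | 7 |
| Day 22 | 15 | 15 |

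These are counts of patterns, not probabilities. The step can act at Day 8 at the earliest, and only where no later score exists. SAP 4.0 sends early discontinuers into a 1-week follow-up, and Table 4-1 schedules a MADRS at Day 22. Anyone who attends that visit has earlier gaps imputed under MAR.

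**Step 5: indirect effect.** Placebo-imputed later values enter the same MMRM and could move the Day 2 contrast through the shared center effect. One simulated dataset used assumed values: 25 per arm, SD 8, correlation 0.6 decaying with visit distance, 5 centers, and 13 active participants shifted by 5 points at Days 15 and 22. The Day 2 contrasts moved by 0.003 to 0.020 points, against a standard error of about 2.2.

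**Step 6: what a real placebo-based step at Day 2 might change.** The documents give no dropout rate, so this is illustration only. In an active arm of 25, each participant with no double-blind score whose Day 2 value is drawn from the placebo model reduces that arm's Day 2 effect by about 1/25 = 4%. For 0, 1 or 2 such participants this is 0%, 4% or 8%.

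**The case against.** The strongest reply is that SAP 10.2 says openly that intermittent gaps are handled under MAR, and that MAR may be quite reasonable for someone who missed Day 2 but was rated later. Both statements stand. The point is not that MAR is wrong for those participants. It is that the SAP does not say this branch takes every Day 2 gap, while still promising an MNAR result there.

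It can also be said that hardly any Day 2 values will be missing. SAP 4.0 fixes Visit 3 one day after Visit 2, footnote a of Table 4-1 brings early discontinuers to a visit with a MADRS, and the Day 2 window nominally reaches Day 7. This stands and limits the size. So does the setting: SAP 14.0 says the sample size was not based on power, and the documents attach no decision to the Day 2 imputation result.

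Two other replies do not help. The rule in SAP 10.3 that fills early gaps with the baseline value serves the responder and remitter models, not the primary endpoint. An mITT participant whose only double-blind score was an unscheduled postdose MADRS on Day 1 would have a monotone gap from Day 2, but no such assessment is planned.

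A reader might infer more than the documents support. One inference is that the primary MMRM estimate is biased; nothing in the documents shows this. Another is that the MNAR step never operates; it does operate on trailing gaps from Day 8. The opposite inference, that all gaps from Day 8 onward are placebo-based, also fails, because any later score, including Day 22, returns a gap to MAR.

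**Conclusion.** The point holds as a mismatch between what the sensitivity analysis is said to do and what its rules do. At Day 2, 0 of 14 possible mITT patterns reach the placebo-based step, so the Day 2 output cannot support a statement that the primary endpoint is robust to MNAR. This follows from the SAP's rules and rests on no assumed rate; it assumes only that no unscheduled postdose MADRS is taken on Day 1. The numerical consequence is probably small and cannot be derived from the documents. It is worth correcting because the output would otherwise carry a wrong label on the primary endpoint, and the correction leaves the primary analysis untouched.

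**What to change.** Amend SAP 10.2, for the sensitivity analysis only:

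- (a) State that all Day 2 gaps in mITT are imputed under MAR, and that later gaps followed by an observed score, including one at Day 22, are too. Do not present the Day 2 result as an MNAR analysis.
- (b) Report by arm the number of missing derived Day 2 values in mITT, and the number of dosed participants outside mITT, split into no MADRS after baseline and Day 22 only.
- (c) If the promised MNAR check of Day 2 is to be kept, add a supplementary run. Impute missing Day 2 values in the active arms from the placebo-based model whether or not later scores exist. Include dosed participants who have a baseline MADRS but no double-blind MADRS after it, also imputed from the placebo-based model. Keep the pooled centers as defined from mITT, with a stated rule for any center that has no mITT participants. Protocol 10.3.1 bases efficacy analyses on mITT and SAP 17.0 currently lists no changes, so record the population change in SAP 17.0.

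Items (a) and (b) cost wording and a few counts per arm. Item (c) costs a small amount of extra imputation work on data already collected, a sensitivity population slightly different from mITT, and possibly a slightly less favourable sensitivity estimate.

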10.3 ADDITIONAL EFFICACY PARAMETERS

Additional efficacy parameters are as follows:

- Change from baseline in Clinical Global Impressions-Severity (CGI-S) at Day 2 (1 day after first dose), Day 8, Day 9 and Day 15
- MADRS responder status at Day 2 (1 day after first dose), Day 8, Day 9, Day 15 and Day 22
- CGI-S responder status at Day 2 (1 day after first dose), Day 8, Day 9 and Day 15
- MADRS remitter status at Day 2 (1 day after first dose), Day 8, Day 9, Day 15 and Day 22
- Time to first response
- Time to first remission

Analysis of change from baseline in CGI-S score will be performed using a similar MMRM to that used for the key secondary parameter. Multiple comparison procedure will not be applied to the above additional efficacy parameters.

Plots of fitted (least squares) mean values and their standard errors based on the MMRM model for the change from baseline in MADRS total score and in CGI-S score, respectively, will be presented by treatment group and by visit.

CGI-S responder is defined as participants achieving a score of ≤ 2 on the CGI-S of Illness scale.

During the randomized treatment period, 2 types of events for MADRS total score will be defined based on the following criteria:

- Responder: $\geq 50\%$ reduction from baseline MADRS total score
- Remitter: MADRS total score ≤ 10

Rates of responders and remitters will be reported by treatment group for each timepoint (Days 2, 8, 9, 15, and 22 after first dose of randomized treatment). A logistic regression model with LOCF imputation will be used to model the probability of a response or the probability of a remission as a function of a treatment group and baseline MADRS or CGI-S total score. The LOCF approach will be used to impute missing postbaseline values, provided that at least 1 postbaseline assessment is available. Missing values between the baseline and the first nonmissing postbaseline will be imputed with the baseline value. If all the postbaseline values are missing, the baseline value will not be carried forward. Only the total score of a parameter will be imputed using the LOCF approach; individual item scores will not be carried forward. Bar charts for the rates of responders and remitters in MADRS total score will be presented by treatment group and by study day.

Descriptive statistics for the first three additional endpoints and their associated statistical testing results from the MMRM models and logistic regression will be respectively presented by visit.

The time to onset of first event (i.e. first response or first remission) is defined as the number of days from the first randomized dosing to the first event. The time to onset in days will be calculated for each type of event (first response or first remission) in person level. Participants who do not meet the criteria for respective type of event will be censored at the time of their last MADRS assessment during the treatment period.

For each type of event, the proportion of participants with onset of first events, Kaplan-Meier estimate in terms of the median time to onset of first event, and its 95% CI will be presented for each treatment group. Plots of the Kaplan-Meier estimate of the distribution of the time to onset of events will also be provided for each treatment arm. Log-rank tests comparing the time to onset of event distribution between each AGN-241751 dose and placebo will be conducted.

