10.3. Statistical Analyses

There will be 2 separate SAPs, 1 each for Part A and Part B. Each SAP will be developed and finalized before database lock for that part of the protocol and will describe in detail the participant populations to be included in the analyses, the safety and efficacy analysis, and the

procedures for accounting for missing or unscheduled data. This section is a summary of the planned statistical analyses of the primary and secondary endpoints.

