10.3.1.1. Primary and Secondary Endpoints (Part A and Part B)

10.3.1.1.1. Part A

The primary and secondary efficacy endpoints are listed below and analyses will be defined in the following sections. All analyses for other efficacy endpoints listed below will be defined in more detail in the SAP for Part A.

Primary efficacy endpoint for Part A of the study:

- Change from baseline (Day 1, predose) in MADRS total score at 1 day after the first dose of treatment (Day 2)

Secondary efficacy endpoint for Part A of the study:

- Change from baseline (Day 1, predose) in MADRS total score at Day 8 and Day 9 after single oral dose, on Day 15 after repeated dose, and on Day 22, 7 days after the completion of AGN-241751 dosing

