10.3.1.3. Additional Efficacy Parameters (Part A and Part B)

10.3.1.3.1. Part A

Additional efficacy parameters are as follows, with the Day 1 (predose) value serving as the baseline:

- Change from baseline in CGI-S total score at Day 2, Day 8, Day 9, and Day 15
- Rate of responders on MADRS or CGI-S at Day 2, Day 8, Day 9, Day 15, and Day 22
- Rate of remitters on MADRS at Day 2, Day 8, Day 9, Day 15, and Day 22
- Time to first response on MADRS
- Time to first remission on MADRS

Analysis of change from baseline in MADRS total score and CGI-S score will be performed using a similar MMRM to that used for the key secondary parameter.

CGI-S responder is defined as participants achieving a score of ≤ 2 on the CGIS of Illness scale.

CGI-S sustained responder: Meet responder criteria at ≥ 2 consecutive visits and continued through to final assessment.

During the randomized treatment period, 4 types of events for MADRS total score will be defined based on the following criteria:

- Responder: $\geq 50\%$ reduction from baseline MADRS total score
- Sustained responder: Meet responder criteria at ≥ 2 consecutive visits and continued through to final assessment
- Remitter: MADRS total score ≤ 10
- Sustained remitter: Meet remitter criteria at ≥ 2 consecutive visits and continued through to final assessment

Rates of responders and remitters will be reported by treatment group for each timepoint of assessment (Day 1 [predose] defined as baseline and Days 2, 8, 9, 15, and 22 after first dose of randomized treatment). A logistic regression model will be used to model the probability of a response or the probability of a remission as a function of a treatment group, and baseline MADRS or CGI-S total score.

The time to onset of first event is defined as the number of days from the first randomized dosing to the first event. The time to onset in days will be calculated for each type of event (response or remission) in person level. Participants who do not meet the criteria for respective type of event will be censored at the time of their last MADRS assessment during the treatment period.

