16.9 CHARACTER VALUES OF CLINICAL LABORATORY PARAMETERS

If the reported value of a clinical laboratory parameter cannot be used in a statistical summary table because, for example, a character string is reported for a parameter of the numeric type, a coded value must be appropriately determined for use in the statistical analyses. The actual values, however, as reported in the database will be presented in the data listings.

[Table 16-3](#) shows examples of how some possible laboratory results should be coded for the analysis.

Table 16-3 Examples of Coding Speci al Character Values for Clinical Laboratory Parameters

Laboratory Test	Possible Laboratory Results (in SI Units)	Coded Value for Analysis
Chemistry: ALT	< 5	5
Chemistry: AST	< 5	5
Chemistry: bilirubin, total	< 2	2
Urinalysis: ketones	> 0	Positive
	≤ 0, Negative	Negative
Urinalysis: pH	> 8.0, ≥ 8.0	8.0
	≥ 8.5	8.5
Urinalysis: glucose	≤ 50	0
	(50, 100]	1+
	(100, 250]	2+
	(250, 500]	3+
	(500, 1000]	4+
	≥ 1000	5+
Urinalysis: protein	≤ 15	0
	(15, 30]	1+
	(30, 100]	2+
	(100, 500]	3+
	≥ 500	4+

ALT = alanine aminotransferase; AST = aspartate aminotransferase; SI = *Le Système International d'Unités* (International System of Units).

17.0

CHANGES TO ANALYSES SPECIFIED IN PROTOCOL

None

18.0 **REFERENCES**

DOCUMENT HISTORY PAGE

Effect Date	Revision Number	Primary Author	Description of Change

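### SAP 10.3 fits response and remission on LOCF scores that can cross a planned change of regimen, and no missing-data sensitivity analysis covers these endpoints

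*SAP*

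**What the plan says.** SAP 10.3 sets the method for the binary endpoints: "A logistic regression model with LOCF imputation will be used to model the probability of a response or the probability of a remission", with treatment group and baseline score as predictors. It then gives two filling rules. For later gaps, "The LOCF approach will be used to impute missing postbaseline values, provided that at least 1 postbaseline assessment is available". For early gaps, "Missing values between the baseline and the first nonmissing postbaseline will be imputed with the baseline value". MADRS response and remission are analyzed at Days 2, 8, 9, 15 and 22. CGI-S response is analyzed at Days 2, 8, 9 and 15.

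Protocol 10.3.1.3.1 gives the same model with no rule for missing values: "A logistic regression model will be used to model the probability of a response or the probability of a remission". Protocol 10.3 assigns to the SAPs the "procedures for accounting for missing or unscheduled data", and Protocol 10.3.1.1.1 adds: "All analyses for other efficacy endpoints listed below will be defined in more detail in the SAP for Part A".

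The primary and secondary MMRM analyses in SAP 10.1 and 10.2 use observed cases. SAP 10.2 also plans a control-based multiple imputation for MADRS change from baseline, for which "50 imputed datasets will be generated". That sensitivity analysis is not extended to the binary endpoints.

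SAP 17.0, headed "CHANGES TO ANALYSES SPECIFIED IN PROTOCOL", reports none.

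**The concern.** LOCF assumes that a participant's score stays where it was last seen. Part A is built so that treatment does not stay the same: one randomized dose, a placebo week, a week of daily randomized dosing, then a week off drug. The Day 15 endpoint is there to describe repeated dosing, and Day 22 to describe the period after dosing ends. A value carried across one of these boundaries reports a different regimen under the later day's label.

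Three things are at stake. The by-visit response and remission results may be biased. The logistic model treats each carried value as an observation, so its standard errors make no allowance for the missing data. And because the planned multiple imputation covers only change from baseline, nothing in the SAP would show how far these results depend on the LOCF assumption.

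**Working it through.** The documents give no dropout rate, response rate or bias figure here, so there is no plan figure to reproduce. The check is a trace through the visit windows, followed by illustrations on stated assumptions.

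**1. Where a carried score comes from (SAP Table 16-1).** The Day 2 window runs from the day after the first dose to the day before the second double-blind dose; if that dose was not received, first dose + 7 days is used. An early-termination score on Day 5 therefore falls in the Day 2 window. If no later score exists in the treatment period, LOCF carries it to Days 8, 9 and 15, so a placebo-week score becomes the repeated-dose result. The Day 9 window extends to 4 days after the second double-blind dose and the last value in it is used, so a carried Day 9 score may follow several daily doses. A termination visit falling in the Day 15 window supplies an observed Day 15 value.

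**2. Day 22.** Early terminators should enter the 1-week follow-up, where MADRS is scheduled, and Table 16-1 appears to assign post-termination visits to Day 22. LOCF reaches Day 22 only if that visit is missed, and only for MADRS.

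**3. Early gaps.** Entry requires MADRS of at least 26 and CGI-S of at least 4 (Protocol 6.1). A carried baseline is a 0% reduction, above the MADRS remission limit of 10 and above the CGI-S response limit of 2. It is always a non-response and a non-remission, including at Day 2. The MMRM leaves the same value missing.

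**4. Bias in one arm's rate.** Bias = m × (p_last − p_target), where m is the share missing at the visit, p_last the response rate at their last observation, and p_target the rate they would have had at the visit. All inputs are assumptions, with m from 4% to 30%.

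| Visit | p_last | p_target | Bias (points) |
|---|---|---|---|
| Day 15 | 10% | 30% | −0.8 to −6.0 |
| Day 15 | 10% | 50% | −1.6 to −12.0 |
| Day 22 | 50% | 40% | +0.4 to +3.0 |
| Day 22 | 50% | 20% | +1.2 to +9.0 |

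The bias is zero if nothing is missing or if response would not have changed after dropout.

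**5. Difference between arms, no true effect.** Assume 35% true Day 15 response in both arms and 10% at the carried visit. LOCF rate = (1 − d) × 0.35 + d × 0.10 for dropout d.
- Dropout 20% v 8%: 0.280 + 0.020 = 30.0% v 0.322 + 0.008 = 33.0%, a false gap of 3.0 points.
- Dropout 25% v 10%: 0.2625 + 0.025 = 28.75% v 0.315 + 0.010 = 32.5%, a false gap of 3.75 points.

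**6. Difference between arms, true effect.** Assume 40% v 20% at Day 15 and 10% at the carried visit in both arms.
- 20% missing in both: 34.0% − 18.0% = 16.0 points instead of 20.0.
- 30% active v 10% placebo: 31.0% − 19.0% = 12.0 points.
- 10% active v 30% placebo: 37.0% − 17.0% = 20.0 points, no bias in the difference.

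Equal dropout is therefore no safeguard, and unequal dropout need not distort the difference.

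**7. Counting missing as non-response instead.** With the assumptions of step 5, the rate is (1 − d) × 0.35.
- 20% v 8%: 28.0% v 32.2%, a false gap of 4.2 points.
- 25% v 10%: 26.25% v 31.5%, a false gap of 5.25 points.

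Both gaps exceed those under LOCF, so non-response imputation is no better as the main method.

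**The case against.** The strongest defense is that the protocol is silent on missing data for these models and delegates both that topic and the detail of the other endpoints to the SAP. LOCF fills a delegated gap, and reporting no changes in Section 17.0 is defensible. This stands. A reader might infer that the SAP contradicts the protocol, particularly because the amendment history records that LOCF was taken out of the efficacy sections. That history describes superseded text, and the current observed-case rule in Protocol 10.3.1.2 covers the primary and secondary endpoints only. Nor is it inconsistent in itself to use observed cases in an MMRM and a filling rule in a logistic model.

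A reader might also infer that LOCF will bias the Day 15 and Day 22 rates, or will favor one arm. Without dropout or response rates the documents do not support that: the illustrations run from zero upward and take opposite signs at the two visits.

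The consequence is limited, and this also stands. These are additional endpoints without multiplicity adjustment, in a part not sized for power. A gap of 3 to 4 points is at most about one participant in an arm of 25 (1/25 = 4 points), against a standard error near 13 points for a difference at rates of 30% (√(2 × 0.3 × 0.7 / 25) = 0.130).

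Finally, SAP 10.3 ties LOCF to the logistic model and does not say whether the descriptive rates and bar charts use it, so contamination of the displayed rates cannot be asserted.

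None of this answers two facts: a carried score can cross a planned regimen change, and these endpoints have no missing-data sensitivity analysis.

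**Conclusion.** The point holds as an inexpensive improvement to the SAP, not as a breach of the protocol. As written, SAP 10.3 can report a single-dose or placebo-week score as the Day 15 repeated-dose result. It forces early gaps to non-response, treats filled values as observed, and offers no check on any of this. The possible bias is of unknown size and sign. The 3.0 and 3.75 point gaps rest on assumed response of 35% and 10% and assumed dropout of 20% v 8% and 25% v 10%; other plausible inputs give anything from zero to about 12 points within an arm. Day 15 is the main exposure. Day 22 is touched for MADRS only, and only when follow-up is missed. The primary and secondary MMRM results do not depend on it.

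**What to change.** In SAP 10.3, derive MADRS response and remission in each of the 50 imputed datasets already planned in SAP 10.2, fit the logistic model in each, and combine by Rubin's rules. State that the result carries the control-based assumption of those datasets. For CGI-S response, specify an analogous multiple imputation of the CGI-S score and apply the response cut-off afterwards; use non-response imputation only as a sensitivity analysis.

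If LOCF is kept, make it a sensitivity analysis and list it in Section 17.0 with a reason. In either case, state which data the descriptive rates and bar charts use.

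The cost is SAP wording and modest programming, including a new imputation model for CGI-S. Conduct and data collection do not change. Estimates may shift slightly in either direction. The change should be made before database lock, by which time Protocol 10.3 requires the SAP to be final.
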